### 3.1.3 Overall Survival

OS is defined as the time from the date of randomization until death due to any cause. Any subject not known to have died at the time of the data cut-off will be censored based on the last recorded date on which the subject was known to be alive.

Note, survival calls may be made in the week following the date of Data Cut Off (DCO) for the analysis, and if subjects are confirmed to be alive or if the death date is after the DCO these subjects will be censored at the date of DCO.

### 3.1.4 Duration of Response

The DoR is defined as the time from the date of first documented response until the date of documented disease progression or death in the absence of disease progression. The end of response should coincide with the date of disease progression or death from any cause used for the PFS endpoint.

For Part 1, DoR will be calculated based on data from the ICR of radiological data. For Part 2 and the Safety lead-in, DoR will be calculated based on the site assessments of radiological data.

The time of the initial response will be defined as the latest of the dates contributing towards the first visit response of PR or CR. For example, if the subject was first noted to have a PR at week 6, and the target and non-target lesions were assessed on different dates at this visit, then the later of the two assessment dates would be used as the start date of the response.

If a subject does not progress following a response, then their DoR will use the PFS censoring time.

Duration of response will not be defined for those subjects who do not have documented response.

### 3.1.5 Disease Control Rate

DCR rate is defined as the number (%) of subjects with at least one visit response of CR or PR, or with stable disease for a minimum of twelve weeks (-5 days) from randomization. Data obtained up until progression, or last evaluable assessment in the absence of progression, will be included in the assessment of DCR. This will be irrespective of whether or not subjects discontinued treatment or received a subsequent therapy prior to progression. For all study parts, the primary assessment of DCR will be based on the FAS. For Part 1, DCR will be calculated based on data from the ICR. For Part 2 and the Safety lead-in, DCR will be calculated from the site radiological data.

### 3.1.6 Tumor Size

The percentage change from baseline in tumor size at Week 12 ( $\% \Delta TS_{Wk12}$ ) is a secondary endpoint for Part 1, and will be used to present waterfall plots of the target lesion data in the Evaluable for Response (EFR) set (see Section 4.3), and also to help evaluate the exploratory objectives of investigating the possible role of HER family expression levels as predictors of clinical benefit. Tumor size is not considered to be a key secondary endpoint; for the purpose of marketing authorization, no statistical claims will be made based on tumor size.

The  $\% \Delta TS_{Wk12}$  will be defined as follows:

- Baseline tumor size (TS): defined as the sum of longest diameters of target lesions at baseline
- Week 12 TS: defined as the sum of longest diameters of target lesions at week 12

$$\% \Delta TS_{Wk12} = 100 \times \frac{Week\ 12\ TS - Baseline\ TS}{Baseline\ TS}$$

An increase from baseline of 20% will be imputed for any subjects who die by any cause, or withdraw from the study due to symptomatic disease progression prior to Week 12 (+5 days). Any subjects who withdraw from the study due to radiological disease progression prior to Week 12 will be included in the analysis, and will be assigned a percentage change from baseline of 20%, or the value that was observed at the time of disease progression (whichever is larger).

The best percentage change from baseline in tumor size ( $\% \Delta TS_{best}$ ) at any time point, will also be calculated and presented using waterfall plots.

The  $\% \Delta TS_{best}$  will be defined as follows:

- Baseline tumor size (TS): defined as the sum of longest diameters of target lesions at baseline
- Best TS: defined as the smallest sum of longest diameters of target lesions as observed at any time point post-randomization up until disease progression (regardless of whether it was a scheduled assessment).

$$\% \Delta TS_{best} = 100 \times \frac{Best\ TS - Baseline\ TS}{Baseline\ TS}$$

Subjects in the EFR set without any evaluable post-randomization target lesion data will be excluded from the waterfall plot of  $\% \Delta TS_{best}$ , except if the subject is known to have died or withdrawn from the study due to symptomatic disease progression prior to Week 12 (+ 5 days), or if non-target lesion or new lesion data is available prior to week 12 (+5 days) which is indicative of disease progression. In such cases, the subject will have an increase from baseline of 20% imputed.

### 3.2 Safety and Tolerability

The safety and tolerability endpoints of the study, including the ECG parameters, are listed in the following sections. Further details of the schedule of assessments for these endpoints can be found in the Clinical Study Protocol.

Due to the non-comparative design and small sample size, the evaluation of the impact of varlitinib on ECG parameters from the Safety lead-in will be considered exploratory.

The primary electrocardiographic analysis of the protocol will be from the time-based ECG analysis performed in Part 1 at baseline, Cycle 1 Day 1, Cycle 1 Day 8, and the safety follow-up visit. Triplicate ECGs will be collected with a PK sample collected immediately following ECG acquisition at the time points outlined in the Clinical Study Protocol. ECGs will be analyzed by a Core ECG Laboratory. The planned methods of analysis for the ECG parameters, including the exposure-response modeling, are outlined in Sections 7.7.3 and 7.11.4.

### 3.2.1 Safety Endpoints

The assessment of safety and tolerability is the primary objective of the Safety lead-in, and a secondary objective of Parts 1 and 2. In all study parts, the safety of varlitinib 300 mg BID in combination with capecitabine, in subjects with BTC, will be assessed using the following endpoints:

- Adverse Events (AEs)
- Vital Signs (blood pressure [systolic and diastolic], heart rate, respiration rate, and body temperature)
- Laboratory assessments (clinical chemistry, hematology, coagulation and urinalysis)
- 12-lead Electrocardiogram (ECG) (P and QRS duration, HR, PR, RR, PQ, QT and QTc intervals using Bazett's and Fridericia's formulae)
- Physical examination (including a standard neurological examination and assessment of weight)

In addition, tolerability will be further explored by assessment of dose reductions, interruptions and modifications (see Section 3.2.2).

Adverse events will be coded by System Organ Class (SOC) and Preferred Term (PT) using the Medical Dictionary for Regulatory Activities (MedDRA) for concomitant diseases and AEs and WHO Drug for medications. All AEs will be evaluated for severity according to NCI-CTCAE version 4.03

Baseline will be defined as the last assessment prior to the start of study treatment. If multiple assessments are performed at the same pre-treatment time point, the mean of the values will be used as the baseline reading.

Specifically, for the ECG assessments, on Day 1, pre-dose is defined as 2 sets of triplicate ECGs taken 45 minutes prior to dosing and approximately 5 minutes prior to dosing. The ECG values from these 2 sets of ECGs will be averaged to create the baseline value. Similarly, for all other time points, for each ECG parameter, each patient's mean will be calculated from the triplicate readings and the mean value will be used.

The ECG parameters of interest include, but are not limited to: QT including QTcF and QTcB, HR (heart or ventricular rate), PR, QRS intervals.

Creatinine clearance will be derived as:

$$eC_{Cr} = \frac{(140 - \text{Age}) \times \text{Mass (in kilograms)} \times \text{Constant}}{\text{Serum Creatinine (in } \mu\text{mol/L)}}$$

where constant=1.23 for males and 1.04 for females, and will be categorized as 30- <60 ml/min, 60-<90 ml/min and =>90 ml/min. Creatinine clearance will be included in summaries of the clinical chemistry data.

QTcB will be derived as:

$$QT_{cB} = \frac{QT}{\sqrt{RR}}$$

QTcF will be derived as:

$$QT_{cF} = \frac{QT}{\sqrt[3]{RR}}$$

For derivation of post-baseline visit values, taking account of possible visit windows, see Section 3.2.1.1.

### **3.2.1.1 General Considerations for Safety Assessments**

Missing safety data will not be imputed. However, safety assessment values of the form of “< x” (i.e., below the lower limit of quantification) or > x (i.e., above the upper limit of quantification) will be imputed as “x” in the calculation of summary statistics but displayed as “< x” or “> x” in the listings.

In order to produce data summaries by visit, visit time windows are required, and will be derived using the following conventions:

- The time windows will be exhaustive so that data recorded at any time point have the potential to be summarized. Inclusion within the time window should be based on the actual date and not the intended date of the visit.
- All unscheduled visit data should have the potential to be included in the summaries.
- The window for the visits following baseline will be constructed in such a way that the upper limit of the interval falls half way between the two visits (the lower limit of the first post-baseline visit will be Day 1). If an even number of days exists between two consecutive visits then the upper limit will be taken as the midpoint value minus 1 day.

Furthermore, the following principles will apply to the presentation of safety data:

- For summaries showing the maximum or minimum values, the maximum/minimum value recorded on treatment will be used (regardless of where it falls in an interval).
- For summaries of the ECG data, the mean value of the triplicate readings will be included in the summaries.
- Listings should display all values contributing to a time point for a subject.
- For visit based summaries:
  - If there is more than one value per subject within a time window then the closest value should be summarized, or the earlier in the event the values are equidistant from the nominal visit date. The listings should highlight the value for that subject that went into the summary table, wherever feasible.
  - For Parts 1 and 2 only, to prevent very large tables or plots being produced that contain many cells with sparse data, for each treatment group, visit data should only be summarized if the number of observations is greater than 1/3 of subjects dosed.

- For summaries at a subject level, all values should be included, regardless of whether they appear in a corresponding visit based summary, when deriving a subject level statistic such as a maximum.
- Baseline will be defined as the last non-missing measurement prior to dosing with study treatment. For laboratory data, any assessments made on day 1 will be considered pre-dose unless explicitly indicated otherwise. Where safety data are summarized over time, study day will be calculated in relation to date of first treatment (which will be termed day 1).

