5.4.6 Procedures for Randomization

Patients must not be randomized unless all eligibility criteria have been met. For Part 1 only, this includes receiving eligibility confirmation from the ICR.

Patients who satisfy all the entry criteria will be centrally assigned to study treatment by the RTSM, according to the randomization scheme generated by the designated CRO. Patients will be randomized in a 1:1 ratio to either varlitinib or placebo, both on a background of capecitabine (n=120 for Part 1 and n=350 for Part 2). The randomization scheme will be stratified by the following 2 covariates:

- Geographical region - US or ROW
- Primary tumor location – gallbladder (GB) or non-GB

The actual treatment given to patients will be determined by the randomization scheme in RTSM. The randomization scheme will be produced using SAS® version 9.4, which incorporates a standard procedure for generating randomization numbers. One randomization list will be produced containing sufficient random numbers for each of the 4 randomization strata. A blocked randomization will be generated and all centers will use the same list in order to minimize any imbalance in the number of patients assigned to each treatment group.

The dose and regimen of randomized therapy to be administered is as follows:

- Varlitinib 300 mg BID, every day
- Placebo BID, every day

Patients in both arms will receive background chemotherapy with capecitabine 1000 mg/m² BID, Day 1 to 14, followed by a 7-day rest period (21-day cycle).

Patients will be identified to the Centralized Randomization Center using site number, screening number, randomization number, gender, and date of birth. Patients will be randomized strictly sequentially within each stratum, as patients are eligible for randomization. The RTSM will inform the Investigator of the Kit ID number to be allocated to the patient at each dispensing visit via electronic data capture (EDC).

Study medication should only be dispensed to each randomized patient at the Cycle 1 Day 1 visit. It is allowed to randomize patient up to 24 hours prior to first dose. The first dose of study medication must only be administered in the morning of Cycle 1 Day 1 after pre-dose assessment (e.g., safety laboratory sampling, electrocardiogram [ECG], PK sampling) are completed. The day on which a patient takes the first dose of study medication will be considered Cycle 1 Day 1.

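### The first post-baseline safety window opens on Day 1, so, read literally, the pre-dose baseline laboratory value can be shown as the first on-treatment value with zero change

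*SAP*

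**What the plan says.** SAP 3.2.1.1 gives these rules for by-visit safety summaries:

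- Coverage: "The time windows will be exhaustive so that data recorded at any time point have the potential to be summarized".
- Assignment: "Inclusion within the time window should be based on the actual date and not the intended date of the visit".
- Lower limit: "the lower limit of the first post-baseline visit will be Day 1".
- Upper limit: halfway to the next visit, with a one-day adjustment when the number of days between the visits is even.
- Selection: if a window holds several values, the one closest to the nominal day is used, and the earlier one if they tie.

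The same section counts study day from the date of first treatment, which is Day 1. It also defines baseline: "Baseline will be defined as the last non-missing measurement prior to dosing with study treatment". It adds: "For laboratory data, any assessments made on day 1 will be considered pre-dose unless explicitly indicated otherwise". Protocol 5.4.6 fits this, since the first dose is "administered in the morning of Cycle 1 Day 1 after pre-dose assessment (e.g., safety laboratory sampling" and other pre-dose assessments) are completed.

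**The concern.** The usual baseline laboratory sample is dated Day 1, and the first post-baseline window includes Day 1. Eligibility is decided by date, with no test of whether the sample was taken before or after dosing. One record can therefore be both the baseline and a candidate for the first on-treatment visit. If it is selected, the change from baseline is 0 by construction.

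This would act as baseline carried forward, although the section opens by saying that missing safety data are not imputed. SAP 7.7.2 plans box plots of change from baseline over time by treatment for Parts 1 and 2, with a reference line at zero. False zeros would fall on that line at the first on-treatment visit. If early loss differed between arms, so would the distortion.

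**Working it through.** The plan gives no figure to reproduce. The check applies the windowing rule to the schedule in Protocol Table 2, first with a lower limit of Day 1 and then of Day 2.

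**Upper limits.** The even-number rule can be read as counting the difference between the nominal days or the days lying between them, so both results are given.

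| Data | First post-baseline visit | Next visit | Midpoint | Window as written |
|---|---|---|---|---|
| Liver tests, Parts 1 and 2 | Day 8 | Day 15 | 11.5 | Day 1 to Day 10 or 11 |
| Part 1 hematology and other chemistry | Day 8 | Day 22 | 15 | Day 1 to Day 14 or 15 |
| Part 2 hematology and other chemistry | Day 22 | Day 43 | 32.5 | Day 1 to Day 31 or 32 |

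**Can the next scheduled visit fill the gap?** No.

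- The Day 15 liver test (±1 day) comes no earlier than Day 14, which is after Day 11.
- Cycle 2 Day 1 (±5 days) comes no earlier than 22 − 5 = Day 17, which is after Day 15.
- Cycle 3 Day 1 comes no earlier than 43 − 5 = Day 38, which is after Day 32.

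**Which value is selected?**

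| Case | Lower limit Day 1 (as written) | Lower limit Day 2 |
|---|---|---|
| Day 8 test missed, nothing else in the window | Day 1, change 0 | none |
| Part 1 Day 8 missed, unscheduled Day 14 value | Day 14 | Day 14 |
| Part 1 Day 8 missed, unscheduled Day 15 value, window to Day 15 | Day 1 | Day 15 |
| Day 8 missed, screening sample used in place of Day 1 | none | none |
| Part 2 Cycle 2 Day 1 missed, no later sample in the window | Day 1, change 0 | none |
| Part 2 Cycle 2 Day 1 missed, end-of-treatment sample on Day 18 | Day 18 | Day 18 |

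The third case is a tie: 15 − 8 = 7 and 8 − 1 = 7. The earlier value wins, so baseline displaces a real on-treatment result. This can arise for tests outside the liver panel, because liver tests have their own Day 15 visit.

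**Size, by assumption.** Let m be the share of values at the first visit that are carried baselines. Assume that these patients would have changed like the others.

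- Reported mean change = (1 − m) × true mean change + m × 0 = (1 − m) × true mean change.
- For m = 0.05, 0.10 and 0.20, the reported mean is 95%, 90% and 80% of the true mean.
- The reported n is 1/(1 − m) times the number with on-treatment data: 1.05, 1.11 and 1.25.

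The planned laboratory change displays are box plots. For medians and quartiles the pull is also toward zero, but its amount depends on the distribution and is not given by (1 − m).

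**The case against.** The best defence is that the SAP already implies the sensible reading. The windows are built for visits that follow baseline, Day 1 laboratory values are classed as pre-dose, and missing safety data are not imputed. A careful programmer could conclude that a baseline record is not a post-baseline value. The Day 1 limit also has a proper use, because Part 1 ECGs are recorded 1.5, 3, 5 and 8 hours after dosing on Day 1. Listings are to highlight the value used where feasible, so a carried baseline would often be visible.

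Much of this stands, and the outcome is possible rather than certain. But the text identifies which visits get windows and does not say which records are ineligible. Two programmers could follow it and produce different displays.

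A reader might infer more than the documents support:

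- *That every missed first test produces a false zero.* It does not. Protocol Table 2, footnote g, lets screening tests within one week replace the Day 1 sample. A closer unscheduled or end-of-treatment value also displaces Day 1.
- *That an early liver signal would be hidden.* The ALT/AST versus bilirubin plots use maximum on-treatment values, and adverse event tables do not use these windows.
- *That the inflated n would defeat the rule limiting visit summaries to those with more than one third of dosed subjects.* With m between 5% and 20%, 80% to 95% of the values counted are real. If nearly all dosed patients have a Day 1 sample, that is far above one third.
- *That vital signs are equally affected.* The Day 1 pre-dose default covers laboratory data only, and the timing of Day 1 vital signs is less clear.

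**Conclusion.** The stated lower limit is wrong for laboratory data as written, and the effect is small. A baseline value can appear as the first on-treatment value when three conditions hold: the rule is applied literally, the patient has a Day 1 sample, and no other value in the window is preferred to it. The reach is limited to visit-based summaries and box plots of values and change from baseline at the first on-treatment visit. The size cannot be fixed from the documents, because they give no missing rate. The 5% to 20% range is an illustration and also assumes that patients who missed the test would have changed like the rest. Efficacy analyses, maximum and minimum on-treatment summaries and adverse event tables are untouched. This is a minor correction worth making before programming.

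**What to change.** Replace the parenthesis in SAP 3.2.1.1 with wording to this effect: *the first post-baseline window opens on Day 2, except that Day 1 assessments with a recorded post-dose time (for example Part 1 ECGs) are assigned by time; baseline and other pre-dose records are never assigned to a post-baseline window.*

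A patient who misses the first on-treatment test then contributes nothing to that visit, in line with the no-imputation rule. The Day 15 tie with baseline disappears, and genuine post-dose Day 1 ECGs are kept. The cost is one SAP sentence, with no new data and no change to study conduct.

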### 2.2.1 Procedures for Randomization

Subjects must not be randomized unless all eligibility criteria have been met.

Subjects who satisfy all the entry criteria will be centrally assigned to study treatment by the RTSM, according to the randomization scheme generated by the CRO. Subjects will be randomized in a 1:1 ratio to either varlitinib or placebo, both on a background of capecitabine. The random scheme will be stratified by the following two covariates:

- Geographical region - US or Rest of World (ROW)
- Primary tumor location – Gall bladder (GB) or non-GB

The actual treatment given to subjects will be determined by the randomization scheme in RTSM. The randomization scheme will be produced using SAS® version 9.4, which incorporates a standard procedure for generating randomization numbers. One randomization list will be produced containing sufficient random numbers for each of the four randomization strata. A blocked randomization will be generated and all centers will use the same list in order to minimize any imbalance in the number of subjects assigned to each treatment group.

The dose and regimen of randomized therapy to be administered is as follows:

- Varlitinib 300 mg twice daily, every day
- Placebo twice daily, every day

Subjects in both arms will receive background chemotherapy with capecitabine 1000 mg/m^2 twice daily, Day 1 to 14, followed by a 7-day rest period (21 day cycle).

Subjects will be identified to the Centralized Randomization Center using site number, screening number, randomization number, gender and date of birth. Subjects will be randomized strictly sequentially within each stratum, as subjects are eligible for randomization. The RTSM will inform the investigator of the Kit ID number to be allocated to the subject at each dispensing visit via electronic data capture (EDC).

For both study parts, the primary and key secondary endpoints will be evaluated using the Full Analysis Set (FAS) based on the intention-to-treat principle.

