## 6. General Statistical Considerations

All statistical analyses will be performed by or under the direct auspices of ASLAN Pharmaceuticals, using SAS®, Version 9.2 or higher.

Unless specified otherwise, data from the Safety lead-in, Part 1 and Part 2 will be presented separately in the Tables, Figures and Listings. Subjects whose data contributed to the Part 1 analysis will not be included in the Part 2 analysis.

The database for the Safety lead-in will be locked at the time of the Part 1 analyses. However, interim data from the Safety lead-in will be made available to the DSMB prior to the final data cut-off (DCO), in order to enable the DSMB to review the emerging safety and tolerability data and to advise whether the study can proceed into Part 1. Details of the data to be provided to the DSMB will be provided in the DSMB charter.

The primary analysis of Part 1 will be the later of 3 months after Last Subject In (LSI) or when 70% of the subjects (84 subjects) have experienced a PFS event. At this point, there will be a formal database lock, and the primary analysis of all primary and secondary endpoints will be performed.

The data cut-off for Part 2 will be when 247 OS events have occurred. All secondary endpoints, including ORR, PFS and DoR, will be reported at the time of the primary analysis of OS.

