### 6.1 Sample Size Estimation

#### 6.1.1 Safety Lead-in

The Safety lead-in is not formally powered to assess any statistical hypotheses. In this part, 12 to 20 eligible subjects (with at least 6 from the US) will be enrolled to receive varlitinib plus capecitabine.

Subjects in this group will be replaced if varlitinib compliance is < 85% in the first 14 days.

#### 6.1.2 Part 1

Part 1 is designed with co-primary endpoints, ORR and PFS. In order to maintain an overall, one-sided 10% type I error rate for Part 1, a **Hochberg** procedure will be used, such that the trial will be deemed to have met its primary objective if either endpoint is significant at the one-sided 5% level, or if both endpoints are significant at the one-sided 10% significance level.

One hundred and twenty subjects provides approximately 80% power to detect a true difference of 17% in response rate, based on a one-sided 5% significance level and assuming 10% response rate for the placebo group and a 27% response rate for varlitinib. To ensure the adequate data are available to evaluate the effects of varlitinib on both co-primary endpoints, the data cut-off for the primary analysis will be the later of 3 months after LSI, and when 70% of subjects (84 subjects) have experienced a PFS event. Based on a minimum of 84 PFS events at the time of the primary analysis,

the trial would have a minimum of 80% power to detect a true HR of 0.58 for PFS, based on a one-sided 5% significance level.

Furthermore, if the primary objective of the study is met, the following approach for type I error control will be applied in order to support marketing approval:

- The overall type I error rate for marketing approval will be controlled at the two-sided 5% level, using a Hochberg procedure
- Using this approach, statistical significance may be claimed if *either* ORR or PFS is significant at the two-sided 2.5% significance level or if *both* ORR and PFS are significant at the two-sided 5% significance level.

One hundred and twenty subjects provides approximately 80% power to detect a true difference of 20% in response rate, based on a two-sided 5% significance level and assuming 10% response rate for the placebo group and a 30% response rate for varlitinib.

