A total of 84 PFS events provides 80% power to detect a true HR of 0.54, based on a two-sided 5% significance level. Assuming an 8 month non-linear recruitment period, a 2.67 month median PFS for capecitabine alone, and a true HR of 0.54, it is estimated that the data cut-off for the primary analysis of Part 1 will occur approximately 12 months after the first subject is randomized into the study (FSI).

### 6.1.3 Part 2

Part 2 is designed with a primary endpoint of OS. Approximately 350 subjects will be randomized into Part 2 to obtain 247 death events (70% maturity). If the true OS HR for the comparison of varlitinib+capecitabine versus placebo+capecitabine is 0.7 (likely to correspond to a 43% prolongation of OS), the study has 80% power to demonstrate a statistically significant difference for OS, assuming a two-sided 5% significance level.

Assuming non-linear recruitment of 350 subjects over a twenty-four month period, and median OS times of 8.6 months and 6 months for the varlitinib and placebo arms respectively, it is estimated 247 OS events will occur approximately 31 months after FSI for Part 2.

All secondary endpoints will be analyzed at the time of the primary analysis of OS.

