### 7.7.2 Clinical Laboratory Data

All clinical laboratory data (clinical chemistry, hematology and urinalysis data), vital signs and ECG data will be listed. In addition, all data measured on a continuous scale (except respiration rate and pulse) will be displayed graphically as described below:

For the Safety lead-in:

- Subject profile plots of laboratory data over time, including reference lines at the LLN and ULN. Any dose reductions will be indicated on the plots using a change in line-type.
- Subject profile plots of the change from baseline over time, including a horizontal reference line at zero. Any dose reductions will be indicated on the plots using a change in line-type.

For Parts 1 and 2:

- Box plots over time, by treatment, including reference lines at the LLN and ULN
- Box plots of the change from baseline over time, by treatment, including a horizontal reference line at zero

To enable assessment of the potential for drug-induced liver injury, for all study parts the following outputs will be produced:

- A scatter plot of maximum on-treatment alanine aminotransferase (ALT) versus maximum on-treatment total bilirubin (x-axis), both expressed as multiples of the upper limit of normal (ULN), including reference lines at 3×ULN for ALT, and 2×ULN for total bilirubin. For each subject, the maximum ALT and maximum total bilirubin may occur at different visits
- A scatter plot of maximum on-treatment aspartate aminotransferase (AST) versus maximum on-treatment total bilirubin (x-axis), both expressed as multiples of the upper limit of normal (ULN), including reference lines at 3×ULN for AST, and 2×ULN for total bilirubin. For each subject, the maximum AST and maximum total bilirubin may occur at different visits.

In the event that the scatter plots of ALT or AST against bilirubin identify any potential Hy's law cases (subjects with either both ALT > 3 x ULN and total bilirubin > 2 x ULN, or both AST > 3 x ULN and total bilirubin > 2 x ULN), profile plots over time will be produced for these subject's liver function tests (ALT, AST, ALP and total bilirubin), expressed in multiples of the ULN, showing all four FLT parameters on the same plot.

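### The one-third display rule is applied arm by arm, so if varlitinib prolongs PFS as planned, about two late visits in Part 1 would be plotted for varlitinib without control (minor).

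*SAP*

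**What the plan says.** SAP 3.2.1.1 sets the rules for by-visit safety summaries. For Parts 1 and 2 it adds that "for each treatment group, visit data should only be summarized if the number of observations is greater than 1/3 of subjects dosed". The stated purpose is to avoid very large tables or plots with sparse cells. The same section exempts subject-level statistics such as maxima, which keep all values, and listings show everything.

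The rule reaches the displays in SAP 7.7.2, which cover continuous laboratory, vital-sign and ECG data apart from respiration rate and pulse. One of them is "Box plots of the change from baseline over time, by treatment, including a horizontal reference line at zero". The by-treatment ECG summaries at each scheduled assessment in SAP 7.7.3 are also visit-based.

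Neither 3.2.1.1, 7.7.2 nor 7.7.3 links the two arms' display at a given visit. The denominator is not explicitly tied to the arm; it is read here as subjects dosed in that arm.

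**The concern.** Both arms receive capecitabine, and treatment ends at progression, toxicity, withdrawal of consent or death (SAP 2.1). Haematology, chemistry and vital signs are taken on Day 1 of each cycle (Protocol Table 2), so the number of observations at a visit follows time on treatment. If one arm progresses faster, it falls below one third first. Its data are still collected but disappear from the plot while the other arm's data remain. The plan expects the faster arm to be control.

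The by-treatment plots exist to set the arms beside each other. Protocol 3.2.2 names rises in transaminases, bilirubin and creatinine as observations with varlitinib. At the latest displayed visits a drift in such values would appear for varlitinib alone, and the reader could not see from the plot whether control patients on capecitabine drifted too.

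**Working it through.** **Inputs.** SAP 6.1.2 assumes "Assuming an 8 month non-linear recruitment period, a 2.67 month median PFS for capecitabine alone, and a true HR of 0.54", and puts the Part 1 cut-off about 12 months after first subject in. Allocation is 1:1, so 60 per arm in Part 1 and 175 in Part 2. Cycles are 21 days. Protocol Synopsis (Sample Size) gives quadratic accrual for Part 2, (i/24)²; applying the same shape to Part 1, (i/8)², is an assumption.

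**The plan's own figures reproduce.** The SAP states: "A total of 84 PFS events provides 80% power to detect a true HR of 0.54, based on a two-sided 5% significance level". Power = Φ(|ln 0.54| × √(84/4) − 1.96) = Φ(2.824 − 1.960) = 80.6%. For HR 0.58 at one-sided 5%, Φ(2.496 − 1.645) = 80.3%. With exponential PFS and quadratic accrual over 8 months, 83.8 events are expected at 12.0 months. The cut-off is "the later of 3 months after Last Subject In (LSI) or when 70% of the subjects (84 subjects) have experienced a PFS event"; 8 + 3 = 11 months comes earlier, so the event count decides.

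**Model.** Varlitinib median = 2.67/0.54 = 4.94 months. At Cycle k Day 1, t = 21(k − 1)/30.44 months. Expected observations = N × 2^(−t/median) × G(t). G is the share of patients entered early enough to reach t before the cut-off T: G = min{1, ((T − t)/R)²}, where R is the accrual period.

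**Part 1** (N = 60 per arm, T = 12, R = 8; more than 20 needed):

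| Visit | t (months) | G | Control | Varlitinib |
|---|---|---|---|---|
| C6 D1 | 3.45 | 1.00 | 24.5 | 37.0 |
| C7 D1 | 4.14 | 0.97 | 19.8 | 32.4 |
| C8 D1 | 4.83 | 0.80 | 13.8 | 24.5 |
| C9 D1 | 5.52 | 0.66 | 9.4 | 18.2 |

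On expected counts, Cycles 7 and 8 are one-armed. In continuous time the arms cross one third at 4.12 and 5.30 months, a gap of 1.18 months, or 1.7 cycles. With uniform accrual the crossings are 4.16 and 5.90 months, or 2.5 cycles. At HR 0.58 the gap is 1.5 (quadratic) to 2.2 (uniform) cycles. In 4,000 simulated trials under the event-driven cut-off the median gap was 2 visits. The 10th to 90th percentile was 1 to 3 (1 to 4 with uniform accrual), and five or more occurred in about 2%.

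**Part 2** (N = 175 per arm, T = 31, R = 24; threshold 175/3 = 58.3). No PFS assumption is given for Part 2; Part 1's is carried over. Control is last shown at Cycle 7 (59.8). At Cycles 8 to 11, G = 1 and control has about 50, 42, 35 and 29. Varlitinib has 66.5 at Cycle 11. At Cycle 12, t = 7.59 and G = (23.41/24)² = 0.951, so it has 175 × 0.345 × 0.951 ≈ 57 and drops out. Four visits are one-armed. The continuous gap is 4.8 cycles (4.9 with uniform accrual), or 4.3 to 4.4 at HR 0.58.

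**Upper bound** (every patient followed to the end, no stopping except progression or death). Time to one third = median × log₂3. That is 2.67 × 1.585 = 4.23 months and 4.94 × 1.585 = 7.84 months. The gap of 3.60 months is 5.2 cycles.

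**Other discontinuation.** Adding an assumed constant hazard in both arms that stops 10%, 20% or 30% by 3 months cuts this upper bound from 5.2 to 3.7, 2.7 or 1.9 cycles.

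**The case against.** The strongest reply is that this is a display choice. It affects no endpoint, test or safety decision, and the SAP gives its reason. All laboratory, vital-sign and ECG data are listed. Subject-level extremes keep every value. Adverse event tables by grade and arm, the maximum ALT and AST against bilirubin plots, and the potential Hy's law profiles are not cut by visit. The laboratory tables in SAP 10.1 are titled as categorical summaries, so for laboratory data the effect falls mainly on box plots. All of this stands.

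A reader might infer that about five cycles of varlitinib data would lack a comparator in Part 1. The documents do not support that. The figure needs about 8 months of follow-up for everyone, whereas 8 months of accrual and a 12-month cut-off leave the last patients about 4 months.

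A reader might also infer that a late laboratory effect could not be judged, or that restoring the control boxes would supply a clean randomised comparison. Neither follows. The control data remain in other outputs, and patients still on treatment late are selected by not having progressed, differently in each arm. The comparison stays descriptive.

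What the reply does not meet is the Part 2 case. There the rule could remove control cells of 29 to 50 patients, which are not the sparse cells it was written to avoid.

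**Conclusion.** The point holds as a minor one. As worded, the rule can leave late by-visit safety displays with varlitinib and no control. The size is about two visits in Part 1 (1.7 to 2.5 cycles at HR 0.54) and about four in Part 2 if the Part 1 PFS assumptions apply there. About five is an upper bound.

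This rests on exponential PFS, the planned HR, treatment ending at progression or death, an assumed accrual shape for Part 1, and the arm-specific reading of the denominator. Stopping for toxicity or withdrawal shortens the gap, as would a smaller PFS effect. End-of-treatment and unscheduled values enter visit windows by date and would move the cut-offs slightly in both arms. No efficacy conclusion is touched.

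**What to change.** Replace the arm-by-arm condition in SAP 3.2.1.1 with a joint one: summarise a visit for both arms whenever either arm has observations from more than one third of the subjects dosed in that arm, and print n per arm at each visit. Make the change before unblinding.

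The cost is one sentence, a flag in the display program, and a few more control boxes with smaller n: about 20 and 14 patients at the two Part 1 visits in the table above. Showing a visit only when both arms pass would also be symmetric. However, it would discard varlitinib boxes of about 32 and 24 patients at those same visits, so the either-arm rule keeps more information.
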